## 3.2 Study endpoints

### 3.2.1 Primary endpoint

- ***The primary endpoint of the phase 1 part*** includes safety and tolerability of EO2401 in combination with nivolumab by a descriptive medical assessment of the combined profile of incidences of adverse events (AEs), treatment-emergent AEs (TEAEs), serious AEs (SAEs), deaths, reasons for treatment discontinuation/delays, and laboratory abnormalities using the NCI-CTCAE v5.0 grading system [60].
- ***The primary endpoint of the phase 2 part*** is the rate of patients without progression (according to iRECIST criteria [37]) or death due to any cause at 6 months after the first dose of randomized treatment. Six months after the first dose of randomized treatment will be determined for each patient and is dependent on the exact time point of evaluation of the CT investigation scheduled at week 25 (day 169). The primary endpoint is to be determined per investigator/local site assessments of progression. The denominator will be all patients who started the randomized treatment in Cohort 2A\* and will be determined for each randomized treatment group separately. Patients will be followed up for progression or death during the first 6 months after start of randomized treatment regardless of whether they stop treatment and continue on other regimens. Patients who

are completely lost to follow-up will be counted as if they had a PFS event during the first 6 months.

\* Cohort 2A = patients with ACC who had prior systemic therapy for established locally advanced or metastatic disease

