For safety and tolerability, the main assessment items in the trial, the selected design is judged to have the possibility to stringently evaluate both early and late toxicity, of importance for an immunization approach, via the demand of thorough assessments of related Grade 3/4 AEs for all patients in all cohorts throughout all study treatments (see general safety rules in [Section 4.2](#)). Also, beside the active safety oversight of the trial by the Investigators (and their teams) in collaboration with the Sponsor via the Medical Monitor (with associated team), an IDMC will support the safety monitoring and give recommendations for possible actions in relation to their assessments of safety events.

[REDACTED] a key parameter for evaluation in the trial is to analyze EO2401-induced immunity and the tests for such analyses [REDACTED] demand [REDACTED] blood for adequate tests to be run

[REDACTED] The future development of EO2401 will be directed by the outcome of the analyses of induced immunity in the early development trials.

[figure not shown]
Preliminary efficacy is also to be assessed in the trial and as indicated RECIST 1.1 [36] and iRECIST [37] criteria will be used for response assessments (local evaluations of response parameters are going to be utilized considering the early development nature of the trial). The basis for this decision is that the novel mechanism of action of the compounds used in the current trial, EO2401 in combination with PD-1 blockade, i.e. a treatment combination aiming at immune and T cell activation, is postulated to lead to unusual patterns of response that might resemble tumor flare [36]. In early trials of immune-based therapeutics in melanoma, investigators described unique response patterns, termed pseudoprogression. Some patients whose disease met the criteria for disease progression based on traditional response criteria such as RECIST (an increase in the sum of measures of target lesions, unequivocal increase in non-target disease, or the appearance of new lesions) were noted to have late but deep and durable responses [36]. Therefore, response and progression in this trial will be evaluated using the revised international criteria (1.1) proposed by the RECIST (Response Evaluation Criteria in Solid Tumors) committee [36] as well as the modified iRECIST guidelines [37].

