### 7.5.2 Post-treatment follow-up before assessed progressive disease; Vnn

Patients who are discontinuing all study treatment without having had confirmation of progressive disease according to iRECIST criteria will be followed [REDACTED] after the latest performed CT assessment during the time period they received study treatment.

At these [REDACTED] timepoints the following will be done:

- a CT for tumor status assessment should be performed and tumor response assessment made, as outlined in [Section 7.7](#),

- documentation of safety; after the post-treatment visit for safety assessment (see [Section 7.5.1](#)) has been made, only SAEs with plausible causal relationship with trial treatment will be documented (in addition, in case of death, an as precise cause of death as possible is going to be documented), and
- if applicable, collection of information regarding further anti-cancer treatments.

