### 8.3 Safety monitoring periods

#### 8.3.1 Reporting

In patients exposed to study treatment, the following must be reported from the date of the patient's signing the ICF until 30 days after the final administration of study treatment:

- AEs regardless of their causal relationship to study treatment,
- SAEs without a plausible causal relationship to study treatment, and
- pregnancy of the patient.

SAEs with a plausible causal relationship to study treatment must be reported from the date of the patient's signing the ICF until indefinitely (regardless of the time elapsed from the final study treatment administration).

In addition, for consistency with nivolumab clinical trial protocols as advised by Bristol-Myers Squibb (marketing authorization holder for nivolumab), collect all non-serious adverse events (not only those deemed to be treatment-related) continuously during nivolumab treatment periods and for a minimum of 100 days following discontinuation of nivolumab treatment. The most conservative approach (longest follow-up) emanating from the two principles (30 days and specifics per above paragraph versus 100 days following discontinuation of nivolumab treatment) should be followed for nivolumab.

In patients not exposed to study treatment, the reporting period for AEs (including SAEs regardless of causal relationship) starts with signature of the ICF and ends:

- the date of the Investigators assessment of "screen failure"-status (see [Section 5.3.2](#)), or
- the date of the patient's consent withdrawal.

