## 4.4 Endpoints

### 4.4.1 Primary endpoint

- Primary endpoint of the phase 1 part includes safety and tolerability of EO2401 in combination with nivolumab by a descriptive medical assessment of the combined profile of incidences of adverse events (AEs), treatment emergent AEs (TEAEs), serious

AEs (SAEs), deaths, reasons for treatment discontinuation/delays, and laboratory abnormalities using the National Cancer Institute-common terminology criteria for AEs (NCI-CTCAE) v5.0 grading system.

- Primary endpoint of the phase 2 part is the rate of patients without progression (according to immune-related Response Evaluation Criteria in Solid Tumors (iRECIST) criteria [Seymour et al]) or death due to any cause at 6 months after the first dose of randomized treatment. Six months after the first dose of randomized treatment will be determined for each patient and is dependent on the exact time point of evaluation of the CT investigation scheduled at week 25 (day 169). The primary endpoint is to be determined per investigator/local site assessments of progression. The denominator will be all patients who started the randomized treatment in Cohort 2A and will be determined for each randomized treatment group separately. Patients will be followed up for progression or death during the first 6 months after start of randomized treatment regardless of whether they stop treatment and continue on other regimens. Patients who are completely lost to follow-up will be counted as if they had a PFS event during the first 6 months.

The evaluation of the primary endpoint is described in Section 7.8.2.

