### 7.11.2 Adverse events (AEs)

AEs will be coded using the MedDRA dictionary version 27.0.

The investigator could assess the relationship of an AE to both study drugs either individually (i.e. for EO2401 and nivolumab separately) or combined (i.e. for both EO2401 and nivolumab together). In context of the intended study treatment, as composed of administered in combination with nivolumab, it is most of the times in principle not possible to make causality assessments for each component by itself (due to the nature of the combination treatment and the mode of action of the components). Only in rare cases (e.g., an AE that appears in the 3-hour time interval between the first injection of EO2401 and the first infusion of nivolumab or in cases where nivolumab administrations have been terminated but treatment continues with EO2401) an individual assessment seems reasonable.

Hence, an AE related to study treatment is defined as any AE with a suspected relationship to EO2401/nivolumab combined, with a suspected relationship to EO2401 alone or a suspected relationship to nivolumab alone or with no information with respect to relatedness (i.e. NA cases).

According to the protocol an AE is considered to be treatment emergent if it is not present when the active phase of the study begins and is not a chronic condition that is part of the patient's medical history, or it is present at the start of the active phase of the study or as

part of the patient's medical history, but the severity or frequency increases during the active phase. The active phase of the study begins at the time of the first dose of the study drug. The active phase of the study ends [REDACTED] after the last study drug administration. Therefore, the following AEs will be considered as not treatment emergent and will be excluded from summary tables:

- AEs starting more than [REDACTED] after last study drug administration
- AEs occurring in patients not treated with EO2401 and/or nivolumab
- AEs starting prior to first study drug administration for that no deterioration in CTCAE grade was documented during the active phase (e.g. patient for that the CTCAE grade improved only)

The following rules will be applied to identify if an AE is regarded as TEAE in case of missing or incomplete start and/or end dates.

- Partial or missing AE start dates will be imputed as follows:

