- Any TEAE leading to interruption of EO2401
- Any TEAE leading to interruption of nivolumab
- Any serious TEAE
- Any serious TEAE related to study treatment

TEAEs, TEAEs related to study treatment, serious TEAEs, serious TEAEs related to study treatment, non-serious TEAEs, LASRs, TEAEs leading to definitive discontinuation of EO2401, and TEAEs leading to interruption of EO2401 will be summarized by the number of events, and the number and percentage of patients, stratified by cohort. In these tables, AEs will be presented by MedDRA PT and grouped by MedDRA SOC. These tables will be sorted by the overall frequency of MedDRA PTs within each MedDRA SOC. An additional table will present TEAEs by MedDRA PT only, and will be sorted by overall frequency of MedDRA PTs.

Furthermore, TEAEs, serious TEAEs, and TEAEs with a worst CTCAE grade of at least 3 will be summarized by the number and percentage of patients per MedDRA SOC and MedDRA PT, stratified by cohort and by worst CTCAE grade. Multiple occurrences of the same AE in the same patient will be counted once using the worst CTCAE grade. In case of missing CTCAE grade the category "missing" will be added. Missing will be counted as the least severe category.

TEAEs [REDACTED] will be summarized by MedDRA PT and grouped by MedDRA SOC for Cohort 1, using the 3-by-3 Evaluable Population.

In addition, time to 1st LASR event will be assessed by a KM-analysis, with censoring if no LASR was reported. If no LASR event was documented, the censoring date will be the date of the latest physical examination with a normal finding for "skin" and "extremities". If no LASR event was documented, and physical examination for extremities was abnormal for baseline and all post-baseline visits, but no change compared to baseline was documented for the post-baseline visits, the censoring date will be the date of the latest physical examination. If no LASR event was documented, and no post baseline

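### Related SAEs that start after the TEAE window are collected without time limit but enter no SAE incidence count described in SAP 7.11.2

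*Protocol*

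**What the plan says.** **Endpoint.** Protocol 3.2.1 defines the phase 1 primary endpoint through the "combined profile of incidences of adverse events (AEs), treatment-emergent AEs (TEAEs), serious AEs (SAEs), deaths, reasons for treatment discontinuation/delays", together with graded laboratory abnormalities. SAP 4.4.1 repeats these components. In both places SAEs are a separate item and are not limited to treatment-emergent events.

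**Collection.** Protocol 8.3.1 states: "SAEs with a plausible causal relationship to study treatment must be reported from the date of the patient's signing the ICF until indefinitely". Protocol 7.5.2 says that after the post-treatment safety visit "only SAEs with plausible causal relationship with trial treatment will be documented", and Protocol 7.5.3 says the same for later follow-up. SAEs without a plausible causal relationship are required to 30 days after the last administration. Non-serious AEs are collected for at least 100 days after nivolumab ends.

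**Window.** Protocol 8.5.1 ends the active phase 100 days after the last study drug. The corresponding figure in SAP 7.11.2 is redacted.

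**Tabulation.** SAP 7.11.2 says "the following AEs will be considered as not treatment emergent and will be excluded from summary tables" and then names, among others, AEs that start after the window. It makes no exception for related SAEs. The overview table has two serious-event rows, one for any serious TEAE and one worded "Any serious TEAE related to study treatment". The SOC/PT tables for serious events are likewise of serious TEAEs and related serious TEAEs. The overview table also has a row for any AE, separate from the row for any TEAE. By-patient listings cover all AEs and all serious AEs without a TEAE limit.

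**The concern.** The protocol asks sites to report related SAEs for as long as they occur, and the endpoint names SAE incidence as a component of its own. The SAP's tables then count serious events only inside the TEAE window. Once the other reporting periods have lapsed, related SAEs are the only safety events still required, so the exclusion falls mainly on events reported because study treatment plausibly caused them.

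The effect runs one way: the tabulated related-SAE incidence can equal what was collected or fall below it, and cannot exceed it. A reader of the study report who takes the related serious row as the related-SAE incidence would not know that later events had been left out by rule.

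**Working it through.** The plan states no figure on this point that could be reproduced. The check sets the text side by side and then sizes one omitted patient.

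**1. What is required, by time since last dose, and where a related SAE goes**

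| Onset | Events required (Protocol 8.3.1, 7.5.2, 7.5.3) | Related SAE in SAP 7.11.2 |
|---|---|---|
| To 30 days | All AEs, all SAEs | Serious TEAE rows and tables |
| 30 to 100 days | Related SAEs; non-serious AEs after nivolumab | Serious TEAE rows and tables, if the SAP window is 100 days |
| After the window | Related SAEs; other events no longer required once their own periods end | Listings; possibly the any-AE row; no SAE count |

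The last row is the gap. It exists for any finite window, so the redacted SAP figure does not affect the argument, only where the gap begins.

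**2. The any-AE row.** Taken at face value it could count a late event, because it is distinct from the any-TEAE row. The exclusion sentence says such events are in no summary table. Both cannot hold, so the section is inconsistent with itself. Even if the row does count late events, it shows neither seriousness nor relatedness.

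**3. Denominators (SAP 4.2).** Non-randomized combination patients: 26 (2A, including 2 from Cohort 1) + 7 (2B) + 13 (3A) + 5 (3B) = 51. Adding the randomized extension, 13 + 2 + 4 = 19, gives 51 + 19 = 70, which matches the total in the Protocol synopsis.

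**4. Effect of one patient.** With x patients counted among n, the tabulated incidence is x/n. One further patient whose only related SAE is late would make it (x + 1)/n. The difference is 1/n.

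| Group | n | 1/n, percentage points |
|---|---|---|
| 2A, non-randomized | 26 | 3.8 |
| 2B | 7 | 14.3 |
| 3A | 13 | 7.7 |
| 3B | 5 | 20.0 |
| All non-randomized | 51 | 2.0 |

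**5. How likely is one such patient?** The documents give no rate of late related SAEs. As an assumption, let each of the 51 patients independently have probability p of being such a patient. The chance of at least one is 1 − (1 − p)^51:

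- p = 1%: 1 − 0.99^51 = 40%
- p = 2%: 1 − 0.98^51 = 64%
- p = 5%: 1 − 0.95^51 = 93%

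These show only that the gap need not be empty. They do not estimate what happened in this trial.

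**The case against.** The strongest reply is that nothing is lost. The endpoint is a descriptive medical assessment and not a single table row. The listings show every serious AE, every event programmed as not treatment-emergent is reviewed at the data review meeting, and with 70 patients listings are workable. A fixed TEAE window also gives near-uniform capture across patients. Much of this stands. A reader might infer that late related SAEs drop out of the endpoint altogether, and the documents do not support that. But the endpoint is an assessment of incidences, a listing gives no incidence, and the data review meeting confirms classification without returning an event to a table.

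Three other stronger readings should be resisted.

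- **A broken promise on late toxicity.** Protocol 4.4 says the design can "evaluate both early and late toxicity, of importance for an immunization approach", but the sentence goes on to tie this to assessments of related Grade 3/4 events throughout study treatment, not long after it. Protocol 1.3.5 describes possible immune-related damage to normal tissue and says nothing about late onset. The point rests on the endpoint and the collection rule alone.
- **Larger effects.** One patient is 7.7 points in Cohort 2A-I (1/13), and 1.5 points among all 66 patients given EO2401 (51 + 13 + 2). Neither sizes the phase 1 endpoint. Safety in the randomized extension is a secondary endpoint, and the 66 include two patients on EO2401 monotherapy, whereas the phase 1 endpoint concerns the combination.
- **An all-cause SAE count without time limit as the true incidence.** Such a count would combine all SAEs early with only investigator-attributed SAEs late.

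It is also fair that SAP Appendices I and II, which hold the full table list and mock-ups, are separate documents not available here. The statement about tables is therefore limited to the text of 7.11.2.

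**Conclusion.** The point holds for related SAEs and should be corrected. As written, SAP 7.11.2 applies a stated rule that leaves late related SAEs out of every SAE incidence count it describes, although SAE incidence is a named component of the phase 1 primary endpoint and these events are collected on purpose. The shortfall is 2.0 percentage points per affected patient in the 51 non-randomized combination patients, always towards a lower rate. The number of affected patients is not in the documents and may be zero.

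The conclusion assumes that the SAP's redacted window is finite (100 days if it follows the protocol) and that the unavailable appendices do not already contain a table of SAEs irrespective of the window.

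**What to change.** In SAP 7.11.2:

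1. Limit the exclusion sentence to the TEAE tables. This also reconciles it with the any-AE row.
2. Add one overview row: any SAE related to study treatment with onset after first dose, irrespective of the TEAE window. Use the section's existing definition of related, which also counts events with no relatedness information.
3. Add one short SOC/PT table of related SAEs starting after the active phase, with time since last dose.

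Do not add an all-cause SAE row irrespective of the window. Protocol 8.3.1 requires unrelated SAEs only to 30 days after last dose, so that row would have no consistent meaning over time.

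The cost is one row and one short table from data already collected, a related-SAE rate that may be slightly less favourable, and a footnote that follow-up after the window differs between patients.

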### 3.2.2 Secondary endpoints

The key secondary objectives of the trial are:

- Percentage of patients with shown immunogenicity

[figure not shown]
to EO2316, EO2317, EO2318, and UCP2 that compose EO2401

[figure not shown]
Cross reactivities with the human TAAs IL13Ra2, FOXM1, and BIRC5/survivin will also be evaluated

[figure not shown]
The other secondary endpoints of the trial are:

- ORR, time to response, and DOR as described by RECIST 1.1 [36] and iRECIST criteria [37]; see [Section 12.1](#) for an outline of response criteria.
- PFS as described by RECIST 1.1 and iRECIST criteria, defined as the time interval from the date of first study treatment administration to the date of progression (by RECIST 1.1 or iRECIST criteria) or death due to any cause, whichever is earlier. Patients without progression or death are to be censored at the time of the last tumor assessment.
- OS defined as the time interval from the date of first study treatment administration to the date of death due to any cause. Patients alive will be censored at the date of the last documented follow-up.
- In addition, in the randomized extension of Cohort 2A safety and tolerability of EO2401/nivolumab will be assessed versus internal concurrent controls (groups of patients treated with EO2401 monotherapy and nivolumab monotherapy, respectively), by incidences of adverse events (AEs), treatment-emergent AEs (TEAEs), serious AEs (SAEs); AEs will be analyzed irrespective of relationship, and as related events.

### 3.2.3 Exploratory endpoints

## 4 STUDY DESIGN

### 4.1 Main study design

This is an open-label, multicenter, phase 1/2 trial to assess safety, tolerability, immunogenicity, and preliminary efficacy of EO2401 in combination with nivolumab for treatment of patients with unresectable, previously treated, and previously untreated, locally advanced or metastatic ACC, or progressive MPP.

[figure not shown]
An extension of Cohort 2A has been made via global amendment 2 (leading to protocol EOADR1-19 version 3.0) including patients with ACC who had prior systemic therapy for established locally advanced or metastatic disease as in the initial part of the study (Cohort 2A non-randomized portion). [REDACTED]

The primary objective of the open-label, randomized, extension of Cohort 2A is to confirm that the retrospectively (in the initial part of the trial) defined inclusion/exclusion criteria can exclude patients with a profile not benefiting from study treatment by determining the effect of EO2401/nivolumab on the progression-free survival rate at 6 months (per investigator/local site assessments). Patients in the extension of Cohort 2A will be randomized 4:1:1 to EO2401/nivolumab, EO2401 monotherapy, and nivolumab monotherapy; patients treated with EO2401 monotherapy and nivolumab monotherapy, respectively, will constitute internal concurrent controls to ensure assay sensitivity in the randomized extension.

[figure not shown]
### 4.2 Overall study design and plan

The trial is a 5-cohort study intended to recruit a maximum of approximately 120 evaluable patients in total:

[figure not shown]
- Cohort 1 (previously treated patients) includes an evaluation by a safety lead-in 3-by-3 design of EO2401 in combination with nivolumab at standard dose; patients with ACC and MPP will be included. Three to 12 evaluable patients will be included depending on the safety profile of the administered treatments.

- Cohorts 2A (previously treated patients) and 2B (previously untreated patients) include an evaluation of EO2401 at the recommended dose found in Cohort 1 in combination with nivolumab in 30 evaluable patients (15 each for Cohorts 2A and 2B) with ACC (note, evaluable patients with ACC from Cohort 1 can be assessed in Cohort 2A as well, leading to the potential need of recruitment of less than 15 patients specifically for Cohort 2A).

- Cohorts 3A (previously treated patients) and 3B (previously untreated patients) include an evaluation of EO2401 at the recommended dose found in Cohort 1 in combination with nivolumab in 30 evaluable patients (15 each for Cohorts 3A and 3B) with progressive MPP (note, evaluable patients with MPP from Cohort 1 can be assessed in Cohort 3A as well leading to the potential need of recruitment of less than 15 patients specifically for Cohort 3A).

Generally, patients evaluable for safety will include all patients who have received at least one dose of EO2401. Patients who are not considered evaluable for safety and did not receive any dose of EO2401 will be replaced (reasons for non-evaluability and pre-treatment safety will be reported; note the replacement strategy is also applied for the randomized extension of Cohort 2A). In addition, in Cohort 1, if for reasons other than safety a patient does not receive 2 doses of EO2401 and complete the [REDACTED] assessment, the patient will not be counted towards the 3-by-3 design and an additional patient should be enrolled (reasons for not being counted towards the 3-by-3 design will be reported, as well as applicable safety findings).

There will be a 2-stage consent procedure for the trial, including a first consent for HLA-typing (or the use of already available information in the patients file; such information even if based on testing before the screening period is acceptable) since a large proportion of the patients will not match the HLA-A2 prerequisite to receive the HLA-A2 specific EO2401 immunization compound. The reason for the initial minimized consent (related to the procedure of HLA-testing, and before testing also establishing based on available information that the patient has ACC or MPP, and an age  $\geq 18$  years) is to spare the necessity of all other testing for possible enrollment in the trial for patients who are not known to be HLA-A2 positive. The second stage of the consent procedure will be related to all other aspects of the trial including procedures.

[figure not shown]
Eligible patients who meet the inclusion criteria and do not meet any of the exclusion criteria and have provided informed consent per above will be enrolled in the study.

The procedures for cohort management and enrollment are outlined in a study specific Charter and also described in [Section 6.8](#).

Patients' data will be collected until the clinical data cut-off (see section 4.3.1); the time will be dependent on when the patient is enrolled in the trial; survival follow-up will be collected until patient's death or sponsor's decision to stop the study( see [Section 4.3](#)); the time of study participation might be shorter in individual patients due to individual patient factors

or general trial conduct decisions (e.g. planned trial termination when reaching a pre-specified follow-up time).

[figure not shown]

[figure not shown]
[figure not shown]
Study treatments will be administered until confirmed tumor progression (iRECIST criteria for confirmed tumor progression are to be used; see [Section 12.1](#)), intolerable toxicity, death, patient or Investigator decision, or planned or early termination of the study (see also [Section 5.3](#)). At the time of stopping study treatment, appropriate other treatment will be advised by the Investigator on an individual patient basis. The patient should continue study follow-up measures for as long as the individual patient consent for follow-up is not withdrawn, the site is open, and the study not terminated per plan, or early.

Of special note, unlike RECIST 1.1, the iRECIST criteria requires the confirmation of progression and uses the terms iUPD (unconfirmed progression) and iCPD (confirmed progression). Confirmatory scans should be performed at least 4 weeks, but no longer than 8 weeks after iUPD. Thus, in the current trial, provided that the individual patient is tolerating the administered treatment adequately, it is allowed continuing trial treatment beyond progression as assessed by the RECIST 1.1. criteria for evaluation of progression according to the iRECIST criteria. Provided good tolerability of the trial treatment and lack of new important symptoms indicating clinical tumor progression the confirmatory scans might be obtained at the current trials planned 8 weekly tumor assessment timepoints.

In the context of confirmation of PD per iRECIST, and the timeline of confirmatory scans to be performed at least 4 weeks, but no longer than 8 weeks after iUPD, it should be specifically noted that in case of any signs of rapidly progressing disease establishment of PD and a following therapy switch should be made also earlier than 4-8 weeks after iUPD when necessary.

For all cohorts, and all patients during the whole trial treatment, the following safety rules will apply:

[figure not shown]

Details of the IDMC process and procedures, and Cohort management plan are outlined in a separate Charters.

The schematic trial and cohort designs are presented in [Figure 6](#) and [Figure 7](#).

[figure not shown]
Protocol No: EOADR1-19  
EudraCT: 2019-003396-19

CONFIDENTIAL

Protocol No: EOADR1-19  
EudraCT: 2019-003396-19

CONFIDENTIAL

